9.1 Informed Consent/Assent Process (in Case of a Minor or Others Unable to Consent for Themselves)	14
10 Literature References	15
Supplements / Appendices	16
Standard Operating Procedure (SOP) Summary of Laboratory Work	16
Standard Operating Procedures Summary (SOP) for Data Collection and Field Work	17
Informed Consent Script to Be Read in Population-Based Field Surveys	18

List of Abbreviations

Alb	Albendazole
APOC	African Programme for Onchocerciasis Control
CFR	Code of Federal Regulations
CRF	Case Report Form
DEC	Diethylcarbamazine
DMID	Division of Microbiology and Infectious Diseases, NIAID, NIH
DSMB	Data Safety Monitoring Board
ELF	Elimination of Lymphatic Filariasis
FWA	Federal-Wide Assurance
GCP	Good Clinical Practice
GPELF	Global Programme to Eliminate Lymphatic Filariasis
IATA	International Air Transport Association
ICH	International Conference on Harmonisation
ICIDR	International Collaboration for Infectious Disease Research
ICT	Immunochromatography Test
IntTrans	Interruption of transmission
IRB	Institutional Review Board
IVER	Ivermectin
LF	Lymphatic Filariasis
MDA	Mass Drug Administration
MF	Microfilaria(e)
OCP	Onchocerciasis Control Programme
OHRP	Office for Human Research Protection
ONCHO	Onchocerciasis
OSHA	Occupational Safety and Health Administration
PELF	Program to Eliminate Lymphatic Filariasis
PI	Principal Investigator
SAE	Severe adverse events
SOP	Standard Operating Procedure
STH	Soil transmitted helminths
WHO	World Health Organization

Protocol Summary

Title: Optimization of Mass Drug Administration with existing drug regimens for Lymphatic Filariasis and Onchocerciasis

Population: Approximately 6,400 people will participate per year. The study population will include females and males over 5 years of age who live in filariasis endemic areas. Subject selection will not be based on health status.

Number of Sites: Two sites in Indonesia (in separate *B. timori* and *W. bancrofti* endemic areas)

Study Duration: 4 years

Subject Duration: Participants will be studied only once in cross-sectional surveys. Some subjects may be included in more than one annual population survey, but this is not a longitudinal study.

Objectives: To evaluate different mass drug administration (MDA) regimens for lymphatic filariasis and its impact on soil transmitted helminthes. MDA is administered by others (e.g., Ministry of Health) and may enhance efforts to control and eliminate these important neglected tropical diseases.

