2.3.2 Potential Benefits

- To subjects:
The study will screen participants for filarial infections and refer infected subjects for free treatment at their local government health center.
- To society:
Participation will provide information on the impact of MDA on filarial and STH infections that affect the public health in the community.

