4 STUDY DESIGN

(Please read this section together with Section 5, “Study Population”)

The project is comprised of repeated annual cross-sectional surveys in sentinel communities before and after initiation of MDA for LF. MDA (standard regimens recommended by WHO) will be provided by government health officials. Data collection will include demographic data, history of lymphedema, scrotal swelling (hydrocele), acute filarial fever or adenolymphangitis, prior treatment for LF. Blood samples (400 µL per person) will be collected from systematically sampled households. Blood will be tested for filarial antigenemia with the Binax Now Filariasis Card Test and Alere Filariasis Strip Test (which detects *Wuchereria bancrofti* antigen in blood, manufactured by Alere, Portland ME, USA). Blood from persons with positive filarial antigen tests will also be tested for microfilaremia (see Section 6 below for methods). The *Brugia* Rapid (BmR1) test will be used to detect antibodies to *Brugia* parasites antibodies in serum or blood samples. Stool examinations will also be performed for diagnosis of STH infections. **Note not all test will be performed on blood and stool samples.**

Safety oversight: Study personnel will monitor subjects for adverse events related to blood collection. No medical monitor or DSMB is needed for this minimal risk, non-intervention study.

Time to collect specimens: Most participants in the community will only be studied once (demographic data, blood, and stool samples). Thus, the **duration** of subject participation will be one day.

Parameters and criteria for assessing the impact of MDA:

Blood tests for *Wuchereria bancrofti* infection, Binax Now Filariasis Card Test and Alere Filariasis Strip Test (with MF testing of antigen positive subjects): We are using these tests as a measure of LF endemicity. The rapid tests detect antigen released from living adult filarial worms potentially capable of resuming MF production in the future. The antigen tests are much more sensitive for *W. bancrofti* infection than tests for microfilaremia. However, antigen tests may

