5 STUDY POPULATIONS

Description of human subject involvement in research:

We will perform repeated annual cross-sectional surveys in study communities.

Eligibility: This project will study people who live in communities that are endemic (or that were endemic at the beginning of the study) for LF. The endemicity rate (MF rate) at baseline should be at least 10% and study areas should have limited or no prior experience with MDA for LF.

Gender, minority and child inclusion: Males and females will be included in population-based village studies without regard to race, religion, or ethnic group. There is no reason to exclude pregnant women and older children from population-based studies. Exclusion of children less than 6 years of age from community studies is justified because prevalence rates for filariasis tend to be very low in young children and because of difficulties associated with collecting clinical specimens from this population.

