7.4 Statistical Analysis Plan

The following outcome variables will be collected and treated as binary variables: Microfilaremia, antigenemia with the Binax Now Filariasis Card Test and/or the Alere Filariasis Strip Test, anti-filarial antibody (*Brugia* endemic area only) and stool parasites (separate analysis for *Ascaris*, *Trichuris*, and Hookworm). Microfilaria counts (recorded as

MF/60 µl smear) and stool egg counts per species (recorded as eggs/gram of feces) will be taken as count variables.

Data will also be collected for demographic characteristics and covariates including age, gender, history of lymphedema, scrotal swelling (hydrocele), and prior treatment for LF.

For demographic characteristics variables, descriptive statistics will be examined for the individuals who participate in the trials by sentinel site (village) and over years of observation. Frequency will be tabulated for categorical variables. Descriptive statistics (mean, median, range and standard deviation) will be obtained for continuous variables.

Impact of MDA on study outcome measures

1. Testing primary hypothesis

The primary hypothesis is that twice annual MDA is superior to annual MDA for eliminating LF. The binary outcome variables used to test this hypothesis include microfilaremia and antigenemia and anti-filarial antibody (*Brugia* endemic area only). The model which is being used will fit a linear trend over time within each village. The mean slope across villages within each treatment group will then allow estimates of time to target levels for control (microfilaremia < .5% and antigenemia < 2%) for a selection of baseline prevalences. To illustrate the analysis strategy, we use antigenemia as an example.

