The antigenemia prevalence is expressed as filarial antigenemia rate (proportion of examined individuals with filarial parasite antigenemia detected with the Binax Now Filariasis Card Test). To estimate the effect of MDA on antigenemia prevalence, we will tabulate mean rates of antigenemia across the four sentinel sites from each treatment zone (annual vs. twice annual MDA) over years of observation including the baseline. A generalized linear mixed model (GLMM) **with a logistic link function** will be used to account for the correlation of observations clustered within the same household from the same sentinel site. The model to estimate the difference in the odds of antigenemia includes treatment regimen and year of observation, and interaction between treatment regimen and year of observation. Some covariates that will be adjusted for in the analysis include sentinel sites, history of lymphedema, scrotal swelling (hydrocele) and prior treatment for LF as well as demographic variables of interest. Modeling will be performed with use of PROC GLIMMIX in SAS 9.2. CONTRAST statements will be used to test the significance of the log odds of antigenemia between the two treatment regimens at each year of observation. The difference of slope of rate decrease between the two regimens over the years of observations will also be tested with CONTRAST statements in PROC GLIMMIX. The resulting estimates will be converted to odds ratios with 95% confidence interval calculated from the robust estimator of variance. The other binary outcome variables (microfilaremia and anti-filarial antibody) will be analyzed with the same technique.

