Treatment coverage rate of the eligible population will be reported from the repeated cross-sectional surveys for the sentinel sites (villages) during different rounds of treatment. Differences in treatment coverage rates will be evaluated between the two treatment regimens (annual vs. twice annual MDA) over time with the use of Chi-square test.

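### The primary regimen-by-year model adjusts for prior LF treatment without a pre-study cut-off; read literally, after baseline this item mostly records the MDA being compared

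*Combined protocol and SAP*

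**What the plan says.** The primary hypothesis is tested in section 7.4 with a generalized linear mixed model containing regimen, year and their interaction. Its contrasts give the regimen comparison at each year and the difference in slope. On adjustment it states: "Some covariates that will be adjusted for in the analysis include sentinel sites, history of lymphedema, scrotal swelling (hydrocele) and prior treatment for LF".

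The treatment item is listed twice as survey data. Section 4 has "Data collection will include demographic data, history of lymphedema, scrotal swelling (hydrocele), acute filarial fever or adenolymphangitis, prior treatment for LF", and section 7.4 repeats it: "Data will also be collected for demographic characteristics and covariates including age, gender, history of lymphedema, scrotal swelling (hydrocele), and prior treatment for LF". Neither place gives a reference date, a look-back window or a coding. Section 4 describes the design as "repeated annual cross-sectional surveys in sentinel communities before and after initiation of MDA for LF", so the question is also put to people who have already been offered study-period MDA.

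Section 5 says that "study areas should have limited or no prior experience with MDA for LF". Section 7.4 has a separate paragraph on uptake: "Treatment coverage rate of the eligible population will be reported from the repeated cross-sectional surveys". It does not say which survey question supplies that rate.

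**The concern.** The regimens differ in how many rounds people are offered. Twice-annual MDA can work through the rounds a person takes and through lower transmission in the community. Whether someone has been treated by the time of a given survey is therefore partly a result of the regimen. Holding it fixed removes some of the difference the trial is meant to estimate, and it compares groups that were formed after the regimens began.

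At stake are the yearly odds ratios and the slope contrast, which are the tests of the primary hypothesis. The definition is also left to whoever codes the variable, possibly after the data have been seen.

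**Working it through.** The plan gives no figure that depends on this covariate, so there is nothing to reproduce. Two questions were worked through. All numerical inputs are assumptions, because the documents give none for this trial; section 2.2 mentions 75% coverage only as background on what counts as high.

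**1. What does a yes after baseline record?** Let c be coverage per round, r the rounds offered and e the share treated before the study. With independent uptake, the share of yes answers that include study-period MDA is

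[1 − (1 − c)^r] / [1 − (1 − e)(1 − c)^r].

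The least favourable case tried was e = 20%, c = 65%:
- r = 1: 0.65 / (1 − 0.80 × 0.35) = 0.65 / 0.72 = 90.3%.
- r = 2: 0.8775 / (1 − 0.80 × 0.1225) = 0.8775 / 0.902 = 97.3%.

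Over e = 0-20% and c = 65-75% the range is 90-100% after one round and 97-100% after two. The item also differs by regimen. At year 1 with e = 0, the share ever treated under one versus two rounds is 65% vs 88% (c = 65%) or 75% vs 94% (c = 75%).

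**2. What does adjustment do to the regimen contrast?** Large-sample logistic regression on expected cell frequencies, for baseline plus three annual surveys, with one round a year versus two. Household and village effects are left out. Inputs: starting prevalence 10%; 10% never treated; everyone else takes each round independently, so that coverage is 60% or 75%. Each round multiplies the odds of infection by m: 0.4-0.6 (strong) or 0.8-0.9 (weak). Weak effects are plausible for antigenemia, since section 4 says antigen can persist for years after microfilaremia clears. The effect runs either (A) wholly through a person's own treatment or (B) half through the zone's average number of rounds.

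Year 1 by hand, for A, m = 0.4, 60% coverage. Uptake among those who ever take treatment is 0.60 / 0.90 = 2/3. Baseline odds are 0.10 / 0.90 = 0.1111, so prevalence after 0, 1 and 2 rounds taken is 0.1000, 0.0426 and 0.0175.
- Annual: 40% took none and 60% took one. Prevalence = 0.4 × 0.1000 + 0.6 × 0.0426 = 0.0655.
- Twice-annual: none 0.1 + 0.9 × (1/3)² = 20%; one 0.9 × 2 × (2/3)(1/3) = 40%; two 0.9 × (2/3)² = 40%. Prevalence = 0.0200 + 0.0170 + 0.0070 = 0.0440.
- Unadjusted odds ratio = (0.0440 / 0.9560) / (0.0655 / 0.9345) = 0.66.
- Within strata, the odds ratio is 1 among the never treated. Among the treated, twice-annual prevalence is (0.0170 + 0.0070) / 0.80 = 0.0300, so the odds ratio is 0.0309 / 0.0444 = 0.70.

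The fitted model has one ever-treated coefficient for all years. Later yes answers stand for more rounds, so that coefficient over-corrects year 1, and the adjusted year-1 odds ratio is 0.91. The log odds ratio retained is ln 0.911 / ln 0.656 = 22%. In the same case the slope odds ratio per year moves from 0.74 to 0.80, with 72% of the log slope retained.

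Full range with yes/no coding (retained = adjusted / unadjusted log-odds slope):

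| Effect per round | Route | Slope retained | Year-1 odds ratio, unadjusted → adjusted |
|---|---|---|---|
| Strong | A | 72-87% | 0.58-0.76 → 0.77-0.92 |
| Strong | B | 88-94% | 0.52-0.74 → 0.58-0.81 |
| Weak | A | 94-99% | 0.85-0.94 → 0.91-0.98 |
| Weak | B | 97-100% | 0.85-0.94 → 0.87-0.96 |

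By year 3 nearly everyone who will ever be treated has been (87-90% vs 90%), and 91-100% of the log odds ratio remains.

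**Direction.** If the never treated have twice the odds of infection, the year-1 odds ratio under A goes from 0.63-0.79 to 0.95-1.07 (strong effects). If they have half the odds and effects are weak, it goes from 0.84-0.94 to 0.82-0.91, mostly away from no difference. If the same people take every round or none, yearly log odds ratios move 0-5% away from zero.

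A second calculation with different assumptions (25% prevalence, odds ratio per round 0.70-0.85, 5% pre-study exposure) retained 90-99% of the slope with ever/never coding and 100% when the covariate was restricted to pre-study treatment.

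**The case against.** The best defence is that prior treatment was meant as background history. Section 5 uses the word prior for experience before the study, the item sits beside lymphedema and hydrocele, and coverage by round is handled in its own paragraph. One undated question could hardly yield coverage by round, so a separate intake question may well exist. The electronic questionnaire is not in the documents, and neither list of survey items claims to be complete. All of this stands: the text shows an undated covariate and does not prove that study MDA will be counted in it. But the benign meaning is stated nowhere, and in repeated surveys the ordinary sense of the item is treatment before the current survey.

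It is also fair that yes/no is the natural coding for a history item, that the slope then changes only modestly, and that unadjusted rates by zone and year will be tabulated. Those tables keep the raw picture visible, but they are not the planned test.

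A reader might infer that adjustment would wipe out the regimen effect. That would need the item coded as a count of rounds, or something similar, and nothing in the documents suggests it.

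**Conclusion.** The point holds as an undefined covariate whose literal reading makes the primary analysis worse. Under yes/no coding the loss of slope is modest: 72-94% retained with strong per-round effects and 94-100% with weak ones. The year-1 contrast is where the distortion matters, and the plan does test each year. These sizes rest wholly on the assumed prevalence, coverage, compliance and per-round effects.

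Two stronger inferences are not supported. One is that the bias must favour no difference. That is the usual direction, but it depends on who goes untreated. It also depends on referral, since "The study will screen participants for filarial infections and refer infected subjects for free treatment at their local government health center" and, from the Protocol Summary, "Some subjects may be included in more than one annual population survey", so infection found at one survey can lead to a yes at the next. The other is that the time-to-target estimates are distorted too: section 7.4 does not say whether those village slopes are covariate-adjusted.

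**What to change.** In section 7.4, leave individual prior LF treatment out of the regimen-comparison models for microfilaremia, antigenemia and antibody, and keep sentinel site and the baseline year. Include the item only if the survey already separates treatment received before the first study MDA round, and then define it that way in the text. Use reported study-MDA intake only for the coverage tables and for an explanatory analysis labelled as such. The count models name no covariates; the same rule should apply if any are added.

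The cost is a line or two of wording. Individual pre-study treatment goes unadjusted, which matters little where earlier MDA is limited or absent. If the restricted item is kept instead, recall after several MDA rounds may be imperfect and could let study treatment back into the covariate, which is why omission is the better default.

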remain positive years after treatment has cleared microfilaremia. The antigen tests will be performed in individual residents over 5 years of age. This will be done by sampling approximately 100 randomly selected households per sentinel site (village) to produce N of 400. There will be 4 sentinel sites for each treatment zone (annual vs twice annual MDA). The target number of samples per village is close to the minimum sample size of 335 needed to show that the rate of antigenemia (card test) positivity is less than 2% (with 95% confidence and 80% power). In post-MDA populations, this corresponds to a MF rate of less than 0.5%, which is an LF elimination target. We expect to collect 4 to 5 blood samples per household. Subjects with positive card tests will be tested for microfilaremia with 60 µl night blood thick smears. Our decision to detect MF by thick smears of finger prick blood rather than membrane filtration of venous blood is because thick smears are recommended for LF elimination program guidelines. In addition, our prior studies in Egypt have shown that L3 production by *Culex* mosquitoes that feed on MF carriers with negative thick smears is negligible. The justification for collecting blood at night for MF testing is that microfilariae of *W. bancrofti* and *B. timori* in Indonesia are nocturnally periodic with highest counts in peripheral blood between 9 p.m. and 2 a.m.

Blood tests for *Brugia timori* infection *B. timori* infections will be detected by two methods, namely microscopic examination and the BrugiaRapid Test (BmR1 antibody) Cassette (Cellabs, Malaysia). Microscopic examination of thick blood smears prepared with 60 µl of blood collected between the hours of 9 p.m. and 2 a.m. The Brugia Rapid test is a rapid diagnostic test kit for detecting antibodies to filarial parasites using serum or whole blood.

Blood samples will be collected from randomly selected households per sentinel site (village) to produce N of 400. There will be 4 sentinel sites for each treatment zone (annual vs twice annual MDA). This sample size number exceeds the minimum target sample size of 335 needed to show that the MF rate is less than 2% (with 95% confidence and 80% power, assuming an actual rate of 0.5%, which is an LF elimination target). We expect to collect 4 to 5 samples per household.

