7.3 Participant Enrollment and Follow-Up

This project aims to enroll approximately 6,400 subjects per year for two study areas (total for *W. bancrofti* and *B. timori* sub-projects). Each of the two study areas (one for *Brugia and Wuchereria (Sikka)* and one for *Wuchereria (Java)*) will have cluster surveys of approximately 400 people per village for 4 villages from annual MDA areas and 400 people per village for 4 villages from twice per year MDA areas.

The community/household surveys are cross-sectional with no follow-up planned.

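### The odds-ratio confidence intervals rest on a robust variance with no named independent unit, small-sample correction or degrees of freedom, although only 4 v 4 villages carry the regimen contrast in each area

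*Combined protocol and SAP*

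**What the plan says.** Section 7.4 fits a logistic mixed model in PROC GLIMMIX with regimen, year and their interaction. CONTRAST statements compare the regimens at each year and compare their slopes. On interval estimation it says: "The resulting estimates will be converted to odds ratios with 95% confidence interval calculated from the robust estimator of variance". Tests are two-sided at 0.05, and the other binary outcomes are handled in the same way.

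Three further statements bear on which unit is independent:

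- The mixed model is meant to "account for the correlation of observations clustered within the same household from the same sentinel site".
- The village enters as an adjustment variable: "Some covariates that will be adjusted for in the analysis include sentinel sites". No village random effect is stated.
- The same section also says "The model which is being used will fit a linear trend over time within each village", and it bases time-to-target estimates on the average village slope in each treatment group.

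On numbers, section 7.3 specifies for each area "4 villages from annual MDA areas and 400 people per village for 4 villages from twice per year MDA areas", at about 400 people per village. Section 4 also gives four sentinel sites per treatment zone. The text supplied contains no small-sample correction, no denominator degrees of freedom and no clustering unit for the robust variance.

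**The concern.** A sandwich variance is trustworthy when there are many independent units. Regimen is a property of the treatment zone a village lies in, so for the regimen comparison the villages are the units, and there are eight per area. With so few, an uncorrected sandwich is biased downwards. It is also itself estimated imprecisely, so a normal cut-off is too tight.

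This is a separate matter from whether the model contains a between-village term. A sponsor could add one, still take the reported interval from an uncorrected sandwich as the sentence allows, and still get intervals that are too short.

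At stake are the regimen odds ratios and the slope difference. These address the primary hypothesis that twice-yearly MDA is superior, and the efficacy results also feed the cost-effectiveness analysis.

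**Working it through.** **Inputs from the document**

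- Villages per regimen per area: k = 4 (sections 4 and 7.3). Check: 2 areas x 8 villages x 400 people = 6,400, which agrees with "This project aims to enroll approximately 6,400 subjects per year for two study areas".
- Nominal coverage 95%; two-sided alpha 0.05 (section 7.4).
- About 100 households and 400 people per village (section 4); 4-year study (protocol summary); baseline MF rate at least 10% (section 5).

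**Closed form, 4 v 4 equal villages.** This takes the favourable case in which the sandwich is clustered on village. The uncorrected sandwich uses divisor k where the unbiased variance uses k - 1, so it is (k - 1)/k = 3/4 of the unbiased value. The reported standard error is therefore sqrt(3/4) = 0.866 of the right one. Comparing |estimate/SE| with a cut-off c is the same as comparing a proper t statistic with 0.866c. That statistic has 2(k - 1) = 6 df when the two arms have equal between-village variance.

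| Reference used | c | 0.866c | P(\|t6\| > 0.866c) | Coverage |
|---|---|---|---|---|
| Normal | 1.960 | 1.697 | 0.141 | 85.9% |
| t, 6 df | 2.447 | 2.119 | 0.078 | 92.2% |

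If one arm's variance dominates, the statistic behaves like t on 3 df. The two coverages become 81.2% and 87.6%.

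The correct half-width is 2.447/1.697 = 1.44 times the one from an uncorrected sandwich with a normal cut-off.

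**Both parts must change.** With an unbiased variance but a normal cut-off, P(|t6| > 1.96) = 0.098, so coverage is about 90%. With a bias-corrected variance and t on 6 df it is 95.0%.

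**Simulation.** Eight villages, 100 households of 4 per village-year, 4 or 5 surveys, no true regimen effect. The documents give no variance components, so these are assumptions on the logit scale: village intercept SD 0.3-0.7, village slope SD 0.1-0.3, household SD 0.7. Starting prevalence was 10-15%. Results are for equal arm variances.

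| Analysis | Coverage, normal | Coverage, t 6 df |
|---|---|---|
| Village mixed model, uncorrected village sandwich | 82-87% | 90-94% |
| Marginal model, uncorrected village sandwich | 77-85% | 85-92% |
| Site fixed effects, slope contrast, uncorrected village sandwich | about 80% | about 88% |
| Sandwich clustered on household | about 20-80% (54% for the slope with site fixed effects) | not tabulated |
| Model-based, random village intercept and slope | 90-93% | 95-97% |

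Model-based intervals need the random slope. With a random intercept only, the slope contrast was covered 59.5% of the time (normal) or 71% (t, 6 df).

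**If both areas were pooled (8 v 8).** The factor is 7/8. With a normal cut-off, P(|t14| > 1.833) = 0.088, so coverage is 91%. With t on 14 df (2.145 x 0.935 = 2.006) the error is 0.065 and coverage 94%. The text does not state that the areas will be pooled.

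**The case against.** The strongest reply is that the plan is incomplete here, not wrong. It says robust, not uncorrected, and a bias-corrected sandwich is also a robust estimator. It states no normal reference. That is fair: an analyst could satisfy the sentence with a sound method. But nothing in the text requires it, and the one correlation unit named, the household, points away from it.

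A reader might infer that the planned intervals cover some 78-86%. The documents do not support that as a description of the plan. The range requires village clustering, no correction and a normal cut-off, none of which is stated, and its lower end also requires assumed between-village SDs. With t on 6 df the balanced figure is 92%. With household clustering the shortfall is usually larger, and the main cause is then village variation left out of the variance, not few-cluster bias.

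A reader might also infer that superiority will be declared falsely at 14% or more. The quoted sentence governs intervals. The tests are assigned to CONTRAST statements whose variance and df are not given, and nowhere does the text say that superiority is judged from these intervals. The inflated error rate follows only if the tests use the same variance.

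What remains is that every uncorrected reading examined gives intervals shorter than they should be.

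**Conclusion.** The point holds, with its size stated conditionally. Section 7.4 sets a variance rule for the regimen odds ratios that does not deliver 95% coverage with 4 v 4 villages unless further choices are made, and it does not make them.

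- **Firm:** in the balanced closed form, an uncorrected village-clustered sandwich covers about 86% (normal) or 92% (t on 6 df). This assumes equal village sizes and equal arm variances, but no value for the between-village SD.
- **Dependent on assumptions:** the simulated 77-87% with a normal reference, and the lower coverage under household clustering, depend on SDs that are not in the documents.
- **Conditional:** false-positive rates of about 14% or 8% apply if the CONTRAST tests share this variance.

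Adding a village term to the model does not remove the problem while the interval still comes from an uncorrected sandwich.

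**What to change.** In section 7.4, name the village as the independent unit for every regimen comparison, and replace the robust-variance sentence with one of the following:

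- **(a)** a small-sample bias-corrected sandwich clustered on village, with t on 6 df per area (8 villages minus 2 regimens); or
- **(b)** model-based intervals from a model with random village intercept and slope, using Kenward-Roger df or df fixed at 6.

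Between-within df should not be offered under (b). Regimen-by-year varies within village, so that rule would give the slope contrast the large within-village df. The reference would then be close to normal, leaving coverage near 90%.

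Apply the same rule to every regimen CONTRAST, both yearly and slope, so that tests and intervals agree. If the areas are to be pooled, say so and restate the df.

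The cost is SAP wording and a procedure option, with no new data. The intervals will be wider: 1.44 times the half-width of an uncorrected village sandwich with a normal cut-off in the balanced case.
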